## 2) Trial design:

Randomized clinical Trial, parallel arms.

Trial framework: Equivalence frame

Allocation ratio: 1:1.

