### **3) Interventions:**

In our study, we selected for both intervention and comparator, materials that don't need from those geriatric bedridden patients to leave their beds with both materials are xylitol containing materials but with different delivery system. The intervention is dissolving xylitol chewable tablets and the comparator is xylitol chewing gum.

The intervention is the newly introduced dissolving xylitol chewable tablets " Listerine Ready Tabs ". Technically, it's a rectangular-shaped, bilayer-compressed tablet that once chewed, creates just enough liquid to swish around your mouth to get a whole-mouth clean feeling. As manufacture claimed the tablet is easy to use just in three simple steps: chew (to activate), swish (to clean), then swallow as unlike mouthwashes which may contain alcohol and other ingredients not intended for ingestion, Listerine Ready Tabs are alcohol-free and safe to swallow which is highly suitable for bedridden patients. It's composed of Xylitol, Erythritol, Isomalt, Calcium Carbonate, Flavor, Magnesium Stearate, Cellulose Gum, Hydroxypropyl Cellulose, Tetrasodium Pyrophosphate, PVP, Sucralose, Acacia Senegal Gum, Potassium Acesulfame, Glycerin, and Potassium Sorbate. Moreover the beneficial effect of xylitol ,as mentioned before, the addition of Erythritol in its composition adds more value for the tablets as all studies strongly support the idea of erythritol as a caries-reducing dietary polyol with inhibitory effect on the growth of certain mutans streptococci isolates by a mechanism of growth inhibition differs from that caused by xylitol. Moreover, combinations of erythritol and xylitol will turn out to exert promising caries-limiting effects in humans as the combined effects may exceed or at least equal the separate effects of both polyols. (*Makinen, 2010*)

The comparator is Original Trident which is a soft gum sweetened with xylitol . It also contains sorbitol, Mannitol, Aspartame, Sucralose and Acesulfame potassium.

For our methodology, the saliva and the dental plaque samples will be collected along the previously determined timeline; **T0**: before taking either the intervention or the comparator and **T1**: immediately after 5min and **T2**: 15days (for salivary ph measurement and bacterial count in both saliva and interdental plaque).

- **For Intervention group:**

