Participants had to take one tablet three times per day, taken orally, after eating. Participants will be directed to chew the tablet (to activate), swish (to clean), then swallow it . They were not to take other probiotic products or mouth rinse throughout the study period. Neither professional prophylaxis nor tooth brushing instruction will be performed before or during the experimental period. (*Nishihara et al, 2014*)

- **For Comparator group:**

Participants were instructed to chew the gum three times daily after eating for 5 min (*Swapnil et al, 2018*).Also ,like the intervention group, they were not to take other probiotic products or mouth rinse throughout the study period and neither professional prophylaxis nor tooth brushing instruction will be performed .(*Nishihara et al 2014*).

- **Salivary sampling:**

On the day of saliva collection, subjects were instructed not to eat or drink anything for at least 1 hour before the collection of saliva sample. The participants were asked to rinse their mouth with water before

collection of saliva to avoid the contamination of food debris. Then, subjects were instructed to let saliva collect without swallowing for at least 1 min, and then to expectorate into sterile graduated collection tube with the help of a sterile funnel. The collected saliva will be divided into two parts : first; at least 2 ml for ph measurement and second; the remaining salivary sample was transferred into 5-ml sterile disposable vials and carried in a vaccine carrier with freezing mixture to the laboratory, where analysis of the sample was done on the same day. *(Swapnil et al, 2018)*

- **Plaque Sampling:**

Interdental plaque samples were collected from mesial and distal surfaces with the help of a sterile spoon excavator. These plaque samples were then dispersed in a test tube containing double de-ionized distilled water. *(Kumar et al 2013)*

- **Salivary ph measurement:**

The pH values were assessed with the help of a pH meter . The required minimum volume of saliva is 2 ml in a sterile test tube so that the bulb of the measuring electrode could dip sufficiently into the saliva samples. Then, collected samples will be then subjected for the pH measurements. *(Kumar et al 2013)*

- **Culture of mutans streptococci:**

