### 1) Outcomes: (*Table 1*)

No.	Outcome Name	score	Criteria	type	Methods of aggregation
1ry	Salivary S.mutans count	VL: very low	10  cfu/ml	Categorical ordinal	Absolute risk will be reported for each intervention independently. Relative risk will be used to compare both interventions with 95 % CI.
		L: low	10  cfu/ml		
M: Moderate	10  cfu/ml				
H: High	10  cfu/ml				
2ry	Interdental plaque Bacterial count	Swapnil et al, 2018			
3ry	Salivary ph	Numerical values	Normal salivary ph = 6.2 - 7.6	Continous	Mean and Standard deviation
		Baliga et al, 2013			

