#### **1.2. Outcome data collection:**

Outcomes will be evaluated by two assessors H.M. & E.M. before interventions, after 5 minutes and 15 days, if both assessors differ in score, they will discuss, if did not agree a third assessor will resolve the conflict.

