### **3) Statistical methods:**

Data will be analyzed using IBM SPSS advanced statistics (Statistical Package for Social Sciences), version 25 (SPSS Inc., Chicago, IL). Categorical data will be described as absolute risk for each intervention independently and relative risk when comparing both interventions. Comparisons between categorical variables will be performed using the chi square test and Kruskal Wallis will be used to test interaction of variables. Continuous data will be described using mean and standard deviation. Comparison between continuous data will be performed using t-test and two-way ANOVA will be used to test interaction of variables. A p-value less than or equal to 0.05 will be considered statistically significant and all tests will be two tailed.

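### Salivary pH is measured three times in each patient, but its interaction test is an ordinary two-way ANOVA with no patient term, which makes the arm-by-visit test too conservative and costs it power

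*Protocol*

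**What the plan says.** All references are to the protocol.

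- **Method.** Section C 3) Statistical methods divides the work on continuous data between two tests. The first is "Comparison between continuous data will be performed using t-test". The second is that "two-way ANOVA will be used to test interaction of variables". The significance rule is "A p-value less than or equal to 0.05 will be considered statistically significant and all tests will be two tailed". The two ANOVA factors are not named. No section mentions a repeated or within-patient factor, a paired test, a patient term or a mixed model.
- **Outcome.** Table 1 under Outcomes classes salivary pH as continuous, summarised by "Mean and Standard deviation". It is the only outcome so classed, and the PICOTS table ranks it third.
- **Schedule.** Outcomes are assessed "before interventions, after 5 minutes and 15 days" (1.2 Outcome data collection). Section 3) Interventions says that samples at these times are "for salivary ph measurement and bacterial count in both saliva and interdental plaque". Table 2 marks sampling and assessment at all three times.
- **Design.** The design is "Randomized clinical Trial, parallel arms" with 1:1 allocation. The sample size section plans 98 patients, 49 per group.

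**The concern.** An ordinary two-way ANOVA assumes that all observations are independent. Here each patient contributes three pH values, and values from one mouth can be expected to correlate. The analysis would take 98 × 3 = 294 values as if each came from a different patient, and would test every effect against one pooled residual.

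The arm-by-visit interaction compares changes within patients. Stable differences between patients cancel out of it, so its proper error is the within-patient variance. The pooled residual still contains the between-patient variance and is too large for this purpose.

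This interaction asks whether the tablet and the gum change pH differently over time, which is close to the stated aim for pH. A test that has lost power will often be non-significant. In a trial whose framework is labelled equivalence, such a result could be misread as showing that the products behave alike.

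**Working it through.** **Inputs from the protocol.** Two arms, three visits and two-sided alpha 0.05. The protocol gives no figure for the pH analysis, so the arm size comes from the sample size section: 29 + 53 = 82, and 82 × 1.2 = 98.4, taken as 98, or 49 per arm. That total was derived for the *S. mutans* categories, not for pH.

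**Assumptions.** The protocol gives neither the within-patient correlation ρ of pH nor its SD or expected difference. I take SD = 1, equal ρ of 0.3, 0.5 or 0.7 between visits, and, for power, an arm difference d = 0.5 SD at 15 days only.

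**Step 1: error terms.**
- Pooled residual: 6 × 49 − 6 = 288 df, expected mean square 1.
- Between-patient: 2 × 49 − 2 = 96 df, expected mean square 1 + 2ρ.
- Within-patient: 2 × 96 = 192 df, expected mean square 1 − ρ.
- Check: [96(1 + 2ρ) + 192(1 − ρ)] / 288 = 1.

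The interaction needs 1 − ρ. The ordinary ANOVA divides by 1, which is too large whenever ρ > 0.

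**Step 2: true size of the interaction test.** In large samples this is P(χ²₂ > 5.99/(1 − ρ)).
- ρ = 0.3: 5.99/0.7 = 8.56, size 1.4%.
- ρ = 0.5: 5.99/0.5 = 11.98, size 0.25%.
- ρ = 0.7: 5.99/0.3 = 19.97, size under 0.01%.

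Simulation (20,000 trials per setting, 49 per arm) gives 1.5%, 0.35% and 0.01%. At ρ = 0 it gives about 5%, as it should.

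**Step 3: power.** The interaction sum of squares due to the effect is n·d²/3 = 49 × 0.25/3 = 4.08, so the noncentrality is λ = 4.08/(1 − ρ), which is 5.83, 8.17 and 13.61. As written, power is P(χ²₂(λ) > 5.99/(1 − ρ)). With the within-patient error it is the noncentral F probability on 2 and 192 df with the same λ.

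| ρ (assumed) | Size as written | Power as written | Power, within-patient error |
|---|---|---|---|
| 0.3 | 1.4% | 37% | 56% |
| 0.5 | 0.25% | 33% | 72% |
| 0.7 | <0.01% | 26% | 92% |

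The simulation placed the 0.5 SD difference at both 5 minutes and 15 days. That pattern gives the same 4.08, and the results agree: 37%, 33%, 26% against 56%, 72%, 92%.

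**Step 4: sensitivity.**
- With 41 per arm (82/2), simulated interaction size is 1.3%, 0.3% and about 0%. Power is 30%, 25%, 17% against 49%, 63%, 86%.
- With unequal correlations (0.8 between the first two visits, 0.3 otherwise) and 49 per arm, the ordinary ANOVA interaction test has size 1.1%. The repeated-measures test has size 6.6% uncorrected and 5.1% with the Greenhouse-Geisser correction, so the correction belongs in the fix.

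**Step 5: the other tests.** In large samples the arm line of the same ANOVA would have size 2[1 − Φ(1.96/√(1 + 2ρ))] = 12%, 17%, 21%. The between-arm t-test at 15 days holds about 5% at every correlation tried.

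**The case against.** **A reader might infer that the plan inflates false claims of a difference between products.** The 12% to 21% figures in step 5 invite this, but the documents do not support it. Statistical methods gives comparisons of continuous data to the t-test and uses the ANOVA for interaction only. The arm line of the ANOVA would mislead only if it were reported. With positive correlation, the test the protocol does assign to the ANOVA errs one way: too few rejections.

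**The independence assumption is read in, not stated.** The protocol names no factors and no error term, and two-way ANOVA is sometimes loose wording for a design with one repeated factor. Sex and medical history are also recorded, so arm and visit are not the only conceivable pair. This stands in part: arm by visit is the literal and likely reading, not a certain one. It does not remove the point. The protocol does not leave the method open for a later plan. It names a specific test that, taken literally, does not fit its own sampling schedule.

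**The outcome ranks low.** This stands. pH is third, the primary outcome is a categorical *S. mutans* count compared by chi-square, and the sample size rests on that outcome.

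**The size rests on assumptions.** This also stands. Correlation and effect are not in the protocol, and equal correlation is doubtful for visits 5 minutes and 15 days apart. The direction does not change in any positive-correlation setting tried. The loss does vary: at ρ = 0.3 it is about a third of the power (37% against 56%), and only at the higher values is it more than half.

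**Conclusion.** The concern holds for the interaction test on salivary pH. If the two-way ANOVA is run as written on arm and visit, it ignores within-patient correlation and is too conservative. Its true size is about 1.4% / 0.25% / under 0.01% in place of 5%, and its power is about 37% / 33% / 26% where 56% / 72% / 92% was available. These figures assume 49 per arm, correlations of 0.3 / 0.5 / 0.7 and a 0.5 SD difference at 15 days only. At zero correlation there would be no loss.

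It does not follow that the comparison between arms is invalid or that the trial's primary conclusion is at risk. A t-test at a single visit remains sound, and the primary outcome does not use this ANOVA. Severity: should be fixed. Confidence is moderate, because the factors are unnamed.

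**What to change.** In section C 3) Statistical methods, replace the two-way ANOVA for continuous data with a repeated-measures analysis of arm, visit and arm by visit, with patient as the subject. Either of two forms will do:

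- a linear mixed model with an unstructured covariance over the three visits; or
- a repeated-measures ANOVA with the Greenhouse-Geisser correction.

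Name arm and visit as the factors. The single-visit t-test may stay; reading the 15-day arm difference from the mixed model is an option, not a necessity.

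The cost is one sentence. Both forms can be run in the SPSS version already named, on the same data, with no added patients or visits.

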## 3) Sample size calculation:

A power analysis was designed to have adequate power to apply statistical test of the research hypothesis that dissolving xylitol chewing tablets will have the better antibacterial effect than xylitol chewing gum against mutans streptococci after 1 month. According to the results of *Swapnil et al. in 2018* in which the probability of bacterial count reduction to  $10^2$  for xylitol chewing gum (comparator) was (0.15), probability of bacterial count reduction to  $10^3$  was (0.6) and probability of bacterial count reduction to  $10^4$  was (0.25) with effect size  $w=0.578$  ( $n=29$ ). If the estimated probability of dissolving xylitol chewing tablets for bacterial count reduction to  $10^2$  is (0.35), probability of bacterial count reduction to  $10^3$  is (0.5) and probability of bacterial count

reduction to  $10^4$  was (0.15) with effect size  $w=0.43$  ( $n=53$ ). By adopting an alpha ( $\alpha$ ) level of 0.05 (5%), power=80%. The predicted sample size ( $n$ ) was a total of (82). Sample size was increased by (20%) to account for possible dropouts during follow-up intervals to be total of (98) cases i.e. (49) for each group. Sample size calculation was performed using G\*Power 3.1.9.2.

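### No usable primary time point is fixed: the primary outcome is assessed at 5 minutes and at 15 days, while the powered hypothesis refers to 1 month, which is not a visit

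*Protocol*

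**What the plan says.** The outcome table (Outcomes, Table 1) ranks "Salivary S.mutans count" first, interdental plaque count second and salivary pH third. The ranking orders outcomes and attaches no time to any of them.

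Outcomes are to be evaluated "before interventions, after 5 minutes and 15 days" (1.2 Outcome data collection). The Interventions section applies the same three times to every outcome: "for salivary ph measurement and bacterial count in both saliva and interdental plaque". The PICOTS list and the participant timeline (Table 2) agree, with T0 at baseline, T1 at 5 minutes and T2 at 15 days.

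Statistical methods gives the test for the ordinal primary outcome, "Comparisons between categorical variables will be performed using the chi square test", and a common threshold: "A p-value less than or equal to 0.05 will be considered statistically significant and all tests will be two tailed". It contains no adjustment and no order of testing, and it does not say whether one visit or both must be significant.

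The Sample size calculation is built on the tablets outperforming "xylitol chewing gum against mutans streptococci after 1 month", at an alpha "level of 0.05 (5%), power=80" per cent. That alpha is not divided between visits.

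**The concern.** The primary time point belongs to the definition of the primary outcome, and the sample size depends on it. Here it cannot be recovered: two visits are eligible, and the one time named in the powered hypothesis is neither of them.

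Two things are at stake. First, the two visits answer different questions. T1 follows a single use by 5 minutes, whereas T2 follows 15 days of use three times a day. With no visit named, the choice between them could be made after the data are seen. Second, if either visit can carry the primary claim, there are two chances of a false-positive result at a threshold that was budgeted for one.

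**Working it through.** **Setting the times side by side**

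| Place in the Protocol | Time for the primary outcome |
|---|---|
| PICOTS; Interventions; Table 2; 1.2 Outcome data collection | 5 minutes and 15 days after baseline |
| Outcomes, Table 1 | none given |
| Research question; Hypothesis | none given |
| Statistical methods | none given; 0.05 two-tailed for all tests |
| Sample size calculation | 1 month |

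No row names one of the two post-baseline visits, and the last row names a time that is not in the schedule. The Review of literature describes the gum trial used for the sample size as a 30-day study sampled at baseline, day 15 and day 30. The 1-month wording may have been carried over from it. The Protocol does not say which day of that trial supplied the response probabilities.

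**The plan's own figure**

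Inputs from the Sample size calculation: gum probabilities 0.15/0.60/0.25 (w = 0.578, n = 29), tablet probabilities 0.35/0.50/0.15 (w = 0.43, n = 53), alpha 0.05, power 80%. A noncentral chi-square calculation with 2 degrees of freedom, taking each w against equal thirds, gives 29 and 53. Then 29 + 53 = 82, and 82 × 1.2 = 98.4, stated as 98. The figure reproduces with one test at one undivided 0.05. Whether those w values are the right basis for comparing two arms is a separate matter.

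**False-positive rate if either visit suffices**

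The Protocol does not give the correlation r between the 5-minute and 15-day results, so r is an assumption and a range is shown.

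- Independent tests: 1 − (1 − 0.05)² = 1 − 0.9025 = 0.0975, or 0.0975 / 0.05 = 1.95 times nominal.
- Correlated two-sided normal tests: 1 − P(|Z₁| < 1.96 and |Z₂| < 1.96).

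| r | Rate for at least one significant result |
|---|---|
| 0 | 9.75% |
| 0.5 | 9.1% |
| 0.8 | 7.8% |

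As a check on the planned test, a three-category chi-square was simulated at both visits on the same patients, with 49 per arm, no true difference and 100,000 trials per setting. For a latent correlation of 0, 0.3, 0.5, 0.7 and 0.9 the rate was 9.9%, 9.8%, 9.7%, 9.5% and 8.6%. The normal approximation therefore does not overstate the size for the planned test.

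**If both visits had to be significant**

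The rate would be 0.05 + 0.05 minus the rate above. That is 0.10 − 0.0975 = 0.25% at r = 0 and 0.10 − 0.078 = 2.2% at r = 0.8. There would be no inflation under that rule.

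**The case against.** The strongest reply is that no two-chance rule is written. The assessment schedules say when samples are taken, not which tests are run. Statistical methods sets a threshold per test and lists no visits. The sample size states one hypothesis at one time with one alpha, which suggests a single late comparison was intended. Multiplicity handling is also commonly left to a statistical analysis plan, and one may exist.

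Most of this stands. A reader might infer that, as written, a difference at either visit counts as a positive primary result, so that the error rate is already nearly doubled. The Protocol does not support that: it has no rule for declaring success, and the inflation depends on how the gap is filled. A reader might also pool all six outcome-by-visit tests into one larger error rate. That would not describe the primary claim, because plaque and pH are already ranked below it, and treating six measurements on the same patients as independent would overstate the total.

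A further limit is that Trial design declares an equivalence frame, whereas the Hypothesis and Sample size calculation describe a test of difference. The rates above apply to the difference test. In an equivalence analysis a significant difference is not the positive result.

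The reply does not remove the contradiction over time. The 1-month reference conflicts with a schedule that ends at 15 days, and this needs no assumption about decision rules. If a single late comparison was intended, the Protocol still does not attach it to a visit that exists. Nor is this only a detail deferred to another document, since the Protocol itself names the wrong time and fixes 0.05 for all tests.

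**Conclusion.** The point holds in this form: the Protocol fixes no usable primary time point, and its sample size refers to a time at which nothing is measured. That part rests on the text alone.

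The effect on the error rate is conditional. If significance at either visit were accepted for the primary claim, the false-positive rate of the difference test would be about 7.8% to 9.75% for an assumed correlation of 0.8 down to 0, against the 5% used in the sample size. If one visit is named, or both are required, there is no inflation.

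This should be corrected before analysis. It does not by itself invalidate the design.

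**What to change.** 1. In Outcomes and Statistical methods, name salivary S. mutans at T2 (15 days) as the single confirmatory comparison at two-sided 0.05. Label the T1 comparison as supportive and keep plaque and pH as secondary. The schedule and the stated interest in an alternative to brushing and rinsing make the later visit the natural choice, but the investigators must confirm it.
2. In the Sample size calculation, change the 1-month reference to the named visit. If the assumed response probabilities come from a different follow-up time, say so and explain why they are used for 15 days.

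The cost is a few sentences. No visit, sample or member of staff is added, and this change leaves the planned 98 as it is. The downside is that a difference seen only at 5 minutes could not be claimed as the primary result.

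If the investigators want both visits to be able to carry the claim, they could test each at 0.025, which gives 1 − 0.975² = 4.94% if independent. By the Protocol's own sample size method that needs 35 + 63 = 98 before dropout, and 98 × 1.2 = 117.6, about 118 patients in place of 98. Naming one visit is much cheaper.

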### **D)Monitoring:**

#### **1) Data monitoring:**

The main supervisor (A.E.) will monitor this study. His role is to monitor any risk of bias from participants, operator or assessors, monitor blinding of the assessors and monitor patient safety, outstanding benefits or harms.

